# 8.3.3 Mechanism/Immunological Analysis

Descriptive statistics and plots (including, but not limited to, those described subsequently) will be used to gain an understanding of the data prior to developing any statistical models. Means, medians, standard deviations, minimums, and maximums will be computed for each

continuous biomarker at each time point for treatment groups and separately for subjects who do/do not experience clinically significant disease reactivation. For dichotomous biomarkers, frequencies and percents will be computed at each time point for treatment groups and separately for subjects who do/do not experience clinically significant disease reactivation. To gain a better understanding of trends over time, summary statistics (e.g., means, medians, or percents) will be plotted versus time at the relevant time points. Plots for individual subjects may also be useful.

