# **3 STUDY DESIGN**

### 3.1 Description of Study Design

This is a Phase II, unblinded, randomized controlled trial of MMF withdrawal in patients with clinically quiescent SLE on longstanding MMF therapy (1000-3000 mg/day for at least one year in the case of extra-renal indication for MMF or for at least two years in the case of renal indications for MMF), who have been on stable doses of MMF, hydroxychloroquine or chloroquine, and corticosteroids (if applicable) for at least 12 weeks prior to randomization, and have an m-SLEDAI of < 4 at screening.

One hundred twenty eligible subjects will be randomized in a 1:1 ratio to one of the two study treatment arms below.

- MMF maintenance arm: These subjects will continue MMF treatment (1000-3000 mg/day) for the rest of their study participation (up to Week 60).
  - Baseline MMF dose = 3000 mg/day
    - Up to 60 weeks on 3000mg/day MMF
  - Baseline MMF dose = 2500 mg/day to 2750 mg/day
    - Up to 60 weeks on 2500mg/day MMF
  - Baseline MMF dose = 2000 mg/day to 2250 mg/day
     Up to 60 weeks on 2000mg/day MMF
  - Baseline MMF dose = 1500 mg/day to 1750 mg/day
     Up to 60 weeks on 1500mg/day MMF
  - Baseline MMF dose = 1000 mg/day to 1250 mg/day
    - Up to 60 weeks on 1000mg/day MMF

- MMF withdrawal arm: These subjects will taper off MMF over 12 weeks and remain off MMF for the rest of their study participation (up to Week 60 or until the primary endpoint of disease reactivation is met, whichever comes first).
  - Baseline MMF dose = 3000 mg/day
    - Four weeks on 1000 mg MMF twice a day (BID)
    - Four weeks on 1000mg (morning) & 500mg MMF (evening) QD
    - Four weeks on 500 mg MMF BID
    - Up to 48 weeks on no MMF
  - Baseline MMF dose = 2500 mg/day to 2750 mg/day
    - Four weeks on 1000mg MMF BID
    - Four weeks on 1000mg (morning) & 500mg (evening) MMF QD
    - Four weeks on 500 mg MMF BID
    - Up to 48 weeks on no MMF
  - Baseline MMF dose = 2000 mg/day to 2250 mg/day
    - Four weeks on 1000mg (morning) & 500mg (evening) MMF QD
    - Four weeks on 500mg MMF BID
    - Four weeks on 500 mg MMF QD
    - Up to 48 weeks on no MMF
  - Baseline MMF dose = 1500 mg/day to 1750 mg/day
    - Four weeks on 500mg MMF BID
    - Four weeks on 500 mg MMF BID
    - Four weeks on 500 mg MMF QD
    - Up to 48 weeks on no MMF
  - Baseline MMF dose = 1000 mg/day to 1250 mg/day
    - Four weeks on 500 mg MMF BID
    - Four weeks on 500 mg MMF QD
    - Four weeks on 500 mg MMF QD
    - Up to 48 weeks on no MMF

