### 3.3.3 Secondary Mechanistic Assessments

• Levels of C3, C4, and anti-dsDNA at Baseline, Week 20, at the time of first flare, and immediately prior to first flare.

- Changes in levels of C3, C4, and anti-dsDNA from Baseline to Week 20, from Baseline to the time of first flare, and from Baseline to the time point immediately prior to first flare.
- Levels of antibodies to Sm, RNP, SSA/Ro, and SSB/La at Baseline.
- Changes in levels of antibodies to Sm, RNP, SSA/Ro, and SSB/La from Baseline to Week 60.
- Levels of interferon-regulated chemokines at Baseline, Week 20, at the time of first flare, and at time points immediately prior to and after first flare.
- Changes in levels of interferon-regulated chemokines from Baseline to Week 20, from Baseline to the time of first flare, and from Baseline to the time points immediately prior to and after first flare.
- Levels of inflammatory and other cytokines at Baseline, Week 20, at the time of first flare and at time points immediately prior to and after first flare.
- Changes in levels of inflammatory and other cytokines at Baseline, Week 20, at the time of first flare and at time points immediately prior to and after first flare.
- Presence/Absence of gene expression patterns (e.g. fingerprint or signature) at Baseline, Week 20, at time of first flare, and at time points immediately prior to and after first flare.
- Change in gene expression patterns from Baseline to Week 20, from Baseline to the time of first flare, and from Baseline to the time points immediately prior to and after first flare.

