#### 6.3.3 **Transcript Profiling Studies**

RNA for transcript analysis will be collected at every scheduled visit and every Flare Visit and stored until the study is completed.

Hypotheses:

- i. Subjects with an "Immunologically Active B Cell Fingerprint" will be more likely to flare than subjects with an "Inactive B Cell Fingerprint";
- ii. Subjects with an "Interferon- $\alpha$  Signature" will be more likely to flare than subjects who lack an Interferon- $\alpha$  Signature.

Transcript profiling for gene expression will be performed on the subset of subjects who flare (estimated at ~15) and matched subjects who do not flare (estimated at 30). For flaring subjects, RNA transcripts will be analyzed at each of 5 time points (Baseline, Week 20, first flare, and the time points immediately prior to and after first flare). For the subjects who do not flare, RNA transcripts will be analyzed at Baseline, Week 20, and time points comparable to the pre-flare, flare, and post-flare time points for matched flaring subjects. All samples will be analyzed at the end of the study, after all flares have been identified. Differences in gene expression at Baseline will be explored among subjects who do and do not flare. In addition, differences in gene expression among treatment arms will also be investigated.

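### By-arm gene-expression summaries would describe a flare-enriched profiled subset, not the randomised arms, because transcripts are measured only in flaring subjects and matched non-flaring ones

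*Protocol*

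**What the plan says.** Protocol 3.3.3 lists, among the mechanistic assessments, "Presence/Absence of gene expression patterns (e.g. fingerprint or signature) at Baseline, Week 20, at time of first flare" and the time points around it. A signature is therefore a dichotomous biomarker.

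Protocol 6.3.3 says that transcript profiling "will be performed on the subset of subjects who flare (estimated at ~15) and matched subjects who do not flare (estimated at 30". Each flaring subject has five time points: Baseline, Week 20, first flare, and the points just before and after it. Non-flaring subjects have Baseline, Week 20 and "time points comparable to the pre-flare, flare, and post-flare time points for matched flaring subjects". The matching factors are not given. The same section adds that "differences in gene expression among treatment arms will also be investigated".

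Protocol 8.3.3 is the only stated plan for summarising these data: "For dichotomous biomarkers, frequencies and percents will be computed at each time point for treatment groups". It also plans separate summaries by reactivation status, and treats continuous biomarkers in the same way. It has no exception for transcripts and no weights.

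The SAP synopsis still lists the gene-expression assessments, but SAP 7.4 covers only C3, C4, anti-dsDNA and antibodies. SAP section 12 records no change on this point.

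**The concern.** The transcript sample is selected on the outcome. Every flaring subject is in it, but only a fraction of the non-flaring ones. A simple percentage by arm then reflects the sampling scheme as well as the arm. If a signature is related to flare, which is what both hypotheses in Protocol 6.3.3 propose, its prevalence in each arm shifts towards the value in flaring subjects. The shift in the difference between arms depends on how the non-flaring subjects were matched, and the plan does not say.

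At stake is the reading of exploratory tables: a percentage labelled as belonging to a treatment group would be taken to describe the 60 subjects randomised to it. Summaries by flare status do not have this problem, apart from any effect of the matching itself.

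**Working it through.** **Inputs from the documents**
- Protocol 3.1: "One hundred twenty eligible subjects will be randomized in a 1:1 ratio to one of the two study treatment arms below", so 60 per arm.
- Protocol 6.3.3: about 15 flaring and 30 non-flaring subjects profiled.
- Protocol 8.1: reactivation risk on maintenance estimated at 0.10 (planning range 0.05 to 0.15); increase with withdrawal 0.05 to 0.15.

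**Assumed, not in the documents**
- 5 flares on maintenance and 10 on withdrawal.
- Signature present in 70% of flaring and 40% of non-flaring subjects, the same in both arms.
- Non-flaring subjects chosen either regardless of arm, or 2:1 within arm.

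**1. The plan's figure of about 15.** Expected events = 60 × maintenance risk + 60 × (maintenance risk + increase).
- 60 × 0.10 + 60 × 0.15 = 6 + 9 = 15.
- 60 × 0.05 + 60 × 0.20 = 3 + 12 = 15.

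The figure is reproduced. The full planning grid gives 9 to 27. The 8 of 80 reported in SAP section 12 scales to 12 of 120.

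**2. Enrichment.** Flaring share of the profiled sample: 15/45 = 33.3%. Share of the trial: 15/120 = 12.5%. Ratio: 2.67. This step uses only the plan's counts. With 30 non-flaring subjects throughout, 9 flares would give 9/39 = 23.1% against 7.5%, and 27 would give 27/57 = 47.4% against 22.5%.

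**3. Effect on arm percentages (assumed scenario).** Percentage = (flaring × 0.70 + non-flaring × 0.40) / total.

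| Sample | Maintenance | Withdrawal | Difference |
|---|---|---|---|
| Full arms | (3.5 + 22)/60 = 42.5% | (7 + 20)/60 = 45.0% | 2.5 |
| Profiled, not matched on arm | (3.5 + 6.29)/20.7 = 47.2% | (7 + 5.71)/24.3 = 52.4% | 5.1 |
| Profiled, matched 2:1 within arm | (3.5 + 4)/15 = 50% | (7 + 8)/30 = 50% | 0 |

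In the second row the 30 non-flaring subjects split as 30 × 55/105 = 15.7 and 30 × 50/105 = 14.3.

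**4. Other assumptions.** At 70% and 30% prevalence:
- 6 versus 9 flares: a full-arm difference of 2.0 points becomes 4.1 (not matched on arm) or 0 (matched).
- 3 versus 12 flares: 6.0 points becomes 12.5 or 0.

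If prevalence is the same in flaring and non-flaring subjects, there is no distortion.

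**5. Against sampling error.** For the second row of the table, standard error = √(0.249/20.7 + 0.249/24.3) = 0.149, or about 15 points. The distortion of 5.1 − 2.5 = 2.6 points is about one-sixth of that.

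**6. Baseline.** The table cannot describe Baseline, where randomisation makes the expected prevalences equal. Suppose instead 45% in both arms and 70% in subjects who later flare. Non-flaring prevalence is then (27 − 3.5)/55 = 42.7% on maintenance and (27 − 7)/50 = 40% on withdrawal. The unweighted profiled sample shows 49.3% versus 52.4% (not matched on arm) or 51.8% versus 50.0% (matched). The true difference is 0; the apparent ones have opposite signs.

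**7. Weights.** Overall sampling fraction of non-flaring subjects: 30/105 = 28.6%, so weight 105/30 = 3.5. Under arm matching the weights differ: 55/10 = 5.5 on maintenance and 50/20 = 2.5 on withdrawal. Weighting by the arm-specific fraction restores 42.5% and 45.0%. A single weight of 3.5 under arm matching would not: (3.5 + 14)/40 and (7 + 28)/80 are both 43.75%.

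**8. Cost in precision.** Effective size = (sum of weights)² / (sum of squared weights).
- Not matched on arm: 3600/(5 + 15.7 × 12.25) = 18.2 of 20.7, and 3600/(10 + 14.3 × 12.25) = 19.4 of 24.3, a loss of about 12% and 20%.
- Matched on arm: 3600/(5 + 10 × 30.25) = 11.7 of 15, and 3600/(10 + 20 × 6.25) = 26.7 of 30, a loss of about 22% and 11%.

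**The case against.** **The objective sets flare aside.** A reader might infer that the third objective in Protocol 2.2.3 would be answered wrongly. The documents do not support that. The objective asks for changes linked to stopping MMF apart from flare. In the table above, the arms have identical prevalence within flare status, so the effect apart from flare is zero and the 2.5 points come only from unequal flare counts. For that objective the arm-matched 50% versus 50% is the right answer, and weighting would bring the flare-driven part back. This stands. It is why the fix includes contrasts within flare status.

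**Weighting has no clear meaning at three of the five time points.** An unsampled non-flaring subject has no flare date, so full-arm prevalence at first flare, or just before or after it, is undefined. This stands, and limits weighting to Baseline and Week 20.

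**Replacing matched controls by random draws within arm is not a wording change.** Different subjects' RNA would be assayed, and any gain from matching for the flare versus no-flare hypotheses would be lost. This stands; the matched selection should stay.

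**The summaries are preliminary and the size is small.** Protocol 8.3.3 presents them as a look at the data before modelling, Protocol 8.5.3 calls the analyses descriptive, and the illustrated bias is well inside the standard error. This is fair on severity. It does not remove the point: a descriptive percentage should describe the group named on its label, and Protocol 6.3.3 does plan an arm comparison.

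**Conclusion.** The concern holds in a limited form. Followed as written, the plan gives by-arm transcript figures for a sample in which flaring subjects are over-represented 2.67-fold, and these do not describe the randomised arms for any signature related to flare. In the illustration a 2.5-point difference becomes 5.1 or 0, depending on an unstated matching rule.

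The enrichment rests on the plan's own counts. The size of the distortion rests on assumed prevalences and an assumed split of flares. Protocol 6.3.3 does not say whether flare means the primary endpoint or any SELENA-SLEDAI flare. The figure of about 15 fits the former, and the enrichment would change under the latter.

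A reader might extend the point to all biomarkers or to the trial's main result. Neither follows. Under Protocol 6.3.1 the Sm, RNP, Ro and La antibodies are measured in all subjects at Baseline and Week 60, and C3, C4 and anti-dsDNA at every scheduled visit. Protocol 6.3.2 does not restrict non-flaring subjects to a matched subset for cytokines. The primary endpoint is untouched. This is a worthwhile refinement of an exploratory analysis.

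**What to change.** Keep the matched selection and add the following to the gene-expression analysis plan:

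- State what counts as a flare for selection, the matching factors (including whether arm is one), and the sampling fraction of non-flaring subjects in each arm or matching stratum.
- At Baseline and Week 20, weight by-arm transcript summaries and arm contrasts by the inverse sampling fraction (1 for flaring subjects; about 3.5 overall for non-flaring subjects, using the arm- or stratum-specific value), with robust standard errors.
- At the pre-flare, flare and post-flare time points, compare arms only within flare status, in line with the objective in 2.2.3. Flare occurs after randomisation, so these contrasts are descriptive.
- Label any unweighted arm percentage as describing the profiled subset only.
- Leave the flare versus no-flare contrast unweighted.

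No extra assays or samples are needed. The cost is the added analysis text, the record of how non-flaring subjects were chosen, and about 12-20% of effective sample size per arm in the weighted summaries (about 11-22% if matching is on arm).

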#### 8.4 Interim Analysis

Interim study results will be reported to the DSMB for planned Data Review Meetings. Reports prepared for these meetings will focus on study conduct and subject safety and may include information on enrollment, randomization, site activation status, protocol deviations, subject status and demographics, and safety analyses. In particular, at each DSMB review, disease reactivation rates in each arm and the risk difference (i.e. risk\_MMFwithdrawal - risk\_MMF maintenance) will be reported along with the 2-sided 95% confidence interval. If the lower 95% confidence limit about the risk difference exceeds 0.40, the DSMB should consider whether or not the study should be stopped for safety concerns. In order to trigger the guidance, the number of disease reactivations in the MMF withdrawal arm must exceed the number in the MMF maintenance arm, but the magnitude of the excess depends on the sample size. Some examples of observed scenarios that would trigger the guidance are as follows:

# Subjects per arm	Minimum # excess reactivations in the MMF withdrawal arm*				
10	7				
20	13				
30	18				
40	23				
50	27				
60	32				
* The excess needed to trigger the guidance also depends on the # of reactivations in the MMF maintenance arm.					

In addition, if  $\leq 10\%$  of the first 80 subjects experience disease reactivation after accruing 60 weeks of post-randomization time and the study is still accruing subjects, then the pooled estimate of the disease reactivation rate may be used to re-estimate the required sample size. The pooled observed rate (and the 2-sided 95% CI) will be used to reconsider the maximum potential difference between the arms. If power is at least 85% under scenarios where the assumed rate in the maintenance arm is  $\leq 5\%$  with an acceptable risk difference of 0.15, then the study team may consider reducing the sample size.

#### **8.5** Other Statistical Considerations

#### 8.5.1 **Covariates**

Covariates that may be considered include, but are not limited to:

- Age
- Race/ethnicity
- SLE duration
- MMF dose at baseline
- MMF use (cumulative mg-year)
- HCQ use (cumulative mg-year)
- Historical organ involvement
- Serological activity at entry (depletion of C3 or C4, presence of dsDNA antibodies)
- Steroid dose at entry
- Disease activity at entry (m-SLEDAI)
- Disease damage at entry, SLICC/ACR Damage Index (SDI)

#### 8.5.2 Multicenter Studies

Because the analyses for this study are largely descriptive, no special consideration of site effects is planned.

#### 8.5.3 Multiple Comparisons and Multiplicity

The primary and secondary analyses for this trial are considered to be descriptive with pvalues and confidence intervals presented as descriptive measures of strength of evidence rather than formal statistical inference. Therefore, no multiplicity adjustments are needed for this study.

#### 8.5.4 **Examination of Subgroups**

To support and further explain findings from the primary and secondary analyses, additional analyses may be conducted for the following subgroups:

- Age
- Race/ethnicity
- Disease manifestation (renal disease/extra-renal disease)
- SLE duration (< 5 years /  $\geq$  5 years)
- Baseline MMF dosing group (<2000 mg per day /  $\ge$  2000 mg per day)

#### 8.5.5 Missing Data

Standard procedures will be used to ensure that data are as complete and accurate as possible. In analyses, a full accounting will be made for all data items. Generally, missing data will be treated as randomly missing with no data imputation. Deviations from this approach will be specified in the Statistical Analysis Plan (SAP). If data are missing for the primary endpoint, sensitivity analyses will be conducted to assess whether conclusions are robust to alternative

analytic approaches for handling these data. If data are missing for other key endpoints, sensitivity analyses could also be conducted, if deemed appropriate. Details of the sensitivity analyses will be provided in the SAP.

#### 8.5.6 **Changes to the Statistical Analysis Plan**

A detailed description of the planned analyses will be provided in a SAP to be completed and signed off prior to the completion of the trial. Major changes from this protocol will be noted in the SAP. If there is sufficient reason to do so, revised plans may be issued during the course of the study. Changes to the SAP that are made subsequent to database lock will be documented in the clinical study report.

# 9 ACCESS TO SOURCE DATA AND DOCUMENTS

Each participating site will maintain the highest degree of confidentiality permitted for the clinical and research information obtained from subjects participating in this clinical trial. Medical and research records should be maintained at each site in the strictest confidence. However, as a part of the quality assurance and legal responsibilities of an investigation, each site must permit authorized representatives of the sponsor, the SACCC, and health authorities to examine (and when required by applicable law, to copy) clinical records for the purposes of quality assurance reviews, audits, and evaluation of the study safety and progress. Unless required by the laws permitting copying of records, only the coded identity associated with documents or other subject data may be copied (obscuring any personally identifying information). Authorized representatives as noted above are bound to maintain the strict confidentiality of medical and research information that may be linked to identified individuals. Participating sites will normally be notified in advance of auditing visits.

All subject records and study documentation will be kept after the protocol is completed. This will include all documentation of AEs, records of study drug receipt and dispensation, and all IRB correspondence. All study records will be kept for at least two years after the investigation is completed.

# 10 DATA COLLECTION, QUALITY CONTROL AND QUALITY ASSURANCE

The investigator is required to keep accurate records to ensure the conduct of the study is fully documented. The period of record retention should be consistent with the record retention policies of the sponsoring agency or applicable regulatory agencies. However, in certain instances, documents should be retained for a longer period if required by the applicable regulatory agency or by the National Institutes of Health.

The investigator will report all protocol deviations to DAIT and the SACCC per the instructions in the ACE Manual of Procedures. The SACCC will forward reports of protocol deviations to the responsible DAIT/NIAID medical officer for review as specified in the ACE Manual of Procedures.

The SACCC is responsible for regular inspection of the conduct of the trial, for verifying adherence to the protocol, and for confirming the completeness, consistency, and accuracy of all documented data.

Data will be obtained from a variety of sources including, but not limited to laboratory notebooks, automated instrument output files, and clinical subject charts. Data from these source materials will be transmitted to the SACCC via one of two mechanisms. Data collected electronically at central laboratories will be transferred electronically directly from the laboratory to the SACCC using standard secure data transfer procedures. Data collected at the clinical sites will be transmitted to the SACCC using an internet-based remote data entry system. Clinical site personnel use an internet browser to key data into e-CRFs; each CRF page is submitted to the clinical database electronically as the page is completed. Univariate data validation tests are performed as the data are keyed. The clinical database is backed up nightly; backup tapes are saved in a secure, off-site location. At any time, authorized site personnel may log in to the remote data entry system, review and correct previously entered data, or key additional data. The data will be further validated per the study data validation plan via a series of computerized and manual edit checks, and all relevant data queries will be raised and resolved on an ongoing basis. Complete, clean data will be frozen to prevent further inadvertent modifications. All discrepancies will be reviewed and any resulting queries will be resolved with the investigators and amended in the database. All elements of data entry (i.e., time, date, verbatim text, and the person performing the data entry) will be recorded in an electronic audit trail to allow all data changes in the database to be monitored and maintained in accordance with federal regulations.

The SACCC will periodically visit the participating clinical sites and audit the source documents in order to validate the data in the SACCC central database. Data will be provided using the subject's screening or enrollment number, the SACCC will not collect personally identifying information such as the subject's name or social security number. Subjects will provide demographic information such as race, ethnicity, and birth date.

Data collected by the SACCC will be held in the strictest confidence, and are protected from access that could reveal personally identifying information about any subject in the trial.

